The aim of the Prediction of Anastomotic Insufficiency risk after Colorectal surgery (PANIC) study is to establish and externally validate an efficient ML-based prediction tool based on multicenter data from a range of international centers.

CR AIS

Clinical Research and Artificial Intelligence in Surgery
Department of Biomedical Engineering, Faculty of Medicine, University of Basel

Methods

Overview

Data is compiled from an assortment of international centers. Principally, the models will be assembled, and publication will be constructed according to the transparent reporting of a multivariable prediction model for individual prognosis or diagnosis (TRIPOD) guidelines. [8] One model will be designed for colon-to-colon anastomosis (PANIC-C) and one distinct separate model will be constructed for colorectal anastomosis (PANIC-R).

The Clinical Research and Artificial Intelligence in Surgery research group, Department of Biomedical Engineering, Faculty of Medicine, University of Basel and the Department of Surgery, Clinic for Visceral and Thorax Surgery, Cantonal Hospital, Winterthur are the sponsors of this study. Dr. med. [name] and [name]. med. [name] are the lead investigators. The lead Ethics committee is the KEK Zürich, associated to the EKNZ, CCER GE, EKOS.

Ethical Considerations

Each center will be accountable for their own ethics board / institutional review board (IRB) approval. They must acquire approval for retrospective or prospective data collection and sharing of the completely deidentified data with the sponsor. The sponsor can assist by providing said protocol, which will also be registered on ClinicalTrials.gov.

Authorship

Each center must share complete data from at least 500 patients to be included. Each cooperating center may assign two center leads and as many contributors as required to enter the data, not exceeding a total of 10 named contributors. Centre leads and center-specific contributors will be listed as full members of the PANIC study group and will be granted PubMed / Medline contributor status in a group authorship model.

Inclusion and Exclusion Criteria

Consecutive patients who underwent colocolic or colorectal anastomosis for neoplasia, diverticulitis, mesenteric ischemia, iatrogenic or traumatic perforation, or inflammatory bowel disease will be included. Patients younger than 18 years of age, who have a recurrent colorectal cancer, beared peritoneal carcinomatosis or unresectable metastatic disease at time of bowel resection and anastomosis, or who could not provide consent to participate according to individual institution's rules will be excluded. Moreover, patients who were lost to follow-up less than six weeks after surgery and who have not noted a successful ostomy reversal will be excluded - in these cases, it cannot be surely assessed whether AI occurred or not.

Data Collection

Each center will assemble their data either prospectively or retrospectively from a dedicated clinical database. Each center must provide data from at least 500 patients over not more than 10 years to be included, this in order to ensure data consistency and centre proficiency as monitored by adequate case load.

A standardized data collection form will be given by the sponsor. The data will be registered in a standardized and deidentified form which ensures data completion and anonymity. A study-specific identifier will be produced upon completion of data entrance of each patient. The study database will not have any identifiable patient data. Contributing centers will maintain a log file in which the study-specific patient numbers can be followed to center-specific patient-numbers, in case of a necessity.

Primary Endpoint Definition

AI (Anastomotic insufficiency/leakage) is defined according to Gessler et al. [6] and Rahbari et al. [9] as any clinical signs of leakage, confirmed by radiological examination, endoscopy, clinical examination of the anastomosis, or upon reoperation.

Secondary Endpoint Definitions

AI will be **graded** retrospectively conferring to the system suggested by Rahbari et al. [9] Anastomosis **takedown** is defined as an interruption of the continuity of the bowel and the formation of a stoma, which will be captured in the database. In cases of AI, **death** will be recorded within 90 days from index surgery. In cases of AI, **time to diagnosis of a leakage** will be calculated as days between the index operation and diagnosis of the leakage by imaging with extraluminal contrast, endoscopy, reoperation, or when fecal containing fluid is objectified in a drainage.

Tertiary Endpoint Definitions

To investigate a potential relationship between AI and oncologic outcomes in a further dedicated study along a 5-year follow-up:

- Disease-free survival (months)
- Overall survival (months)
- Adjuvant/additive immunochemotherapy (yes/no)
- Adjuvant/additive radiotherapy (yes/no)
- Additive curative surgery (no/yes: liver; lung; locoragional relapse)

Features and Their Definitions

All features are measured preoperatively within 30 days of index surgery. The following data will be collected.

For colon-to-colon anastomosis:

- Active smoking (yes/no, pack/years) [10, 11]
- Alcohol abuse (>2 alcoholic beverages per day) [11]
- Height / Weight / BMI [5]
- Preoperative leukocyte count (in $\times 10^3$ per mm^3) [7]
- Preoperative steroid use (mg) [3, 4]
- Preoperative non steroidal inflammatory drug use (NSAID)
- Neoadjuvant chemotherapy (yes/no)
- Charlson Comorbidity Index (CCI) [12]
- American Society of Anesthesiologists (ASA) Score [13-15]
- Renal function (CKD Stages G1 (normal) to G5) [7]
- Nutritional status (NRS ≥ 3) [16]
- Hypoalbuminemia (<3.5 g/dL) [17-19]
- Hemoglobin level (in g/dL) [20, 21]
- Prior abdominal surgery (any) [22]
- Liver metastasis at time of anastomosis (any) [22]
- Age (yrs.)
- Albumin and Prealbumin
- Perioperative blood transfusion
- Psychosocial diseases
- Gender (M/F) [12, 15, 18, 22, 23]
- Anastomotic configuration (stapler anastomosis, stapled and suture closure of stapler enterotomy, hand-sewn; end-to-end; side-to-end; pouch to end)
- Emergency surgery (yes/no)
- Approach: Laparoscopic, transanal, robotic, open
- Extended resection
- Conversion to laparoscopic/open surgery (yes/no)
- Left hemicolectomy / right hemicolectomy / extended left hemicolectomy / extended right hemicolectomy / ileocaecal resection / transverse colectomy / sigmoid resection
- Perforation (yes/no; when yes within 5cm from tumor (yes/no))
- Protective ostomy (yes/no)
- Intra- and postoperative complications

- Date of discharge and discharge status
- Postoperative leucocyte count and CRP level up to 10 days postoperative
- Oncologic resection (yes/no; requires at least 12 LN and integrity of mesocolic/mesorectal planes)
- Indication (Neoplasia, IBD, perforation, diverticulitis, mesenterial ischemia)
- In case of colon cancer, preoperative carcinoembryonic antigen (CEA, ng/ml) and pathological TNM staging according to TNM 8th edition (T, N, M, L, V, Pn, grading (high, low), resection status (R0, R1, R2)
- In case of colon cancer length of follow-up, disease-free and overall survival

For colo-rectal anastomosis:

- Preoperative tumor stage (MRI): Local (cT) [24-26]
- Preoperative tumor stage (MRI): Nodal (cN) [24, 26]
- Preoperative circumferential and distal margins (MRI)
- Preoperative endovascular margin (MRI)
- Preoperative tumor stage (CT thorax abdomen): Metastasis (cM) [24, 26]
- Neoadjuvant radiotherapy (yes/no) [26-28]
- Neoadjuvant chemotherapy (yes/no)
- Active smoking (yes/no, pack/years) [11, 29]
- Alcohol abuse (>2 alcoholic beverages per day) [11, 30]
- Height / Weight / BMI [31]
- Preoperative leukocyte count (in $\times 10^3$ per mm^3) [7]
- Preoperative steroid use (mg) [3, 4, 32]
- Preoperative non steroidal inflammatory drug use (NSAID)
- Charlson Comorbidity Index (CCI) [12]
- American Society of Anesthesiologists (ASA) Score [13, 14, 32]
- Renal function (CKD Stages G1 (normal) to G5) [7, 33]
- Nutritional status (NRS ≥ 3) [16, 34]
- Hypoalbuminemia (<3.5 g/dL) [17-19]
- Hemoglobin level (in g/dL) [20, 21, 35]
- Prior abdominal surgery (any) [22]
- Age (yrs.)
- Albumin/Prealbumin
- Perioperative blood transfusion
- Psychosocial diseases
- Liver metastasis at time of anastomosis (any) [22]
- Gender (M/F) [12, 18, 22, 26, 27, 34, 36, 37]

- Emergency surgery (yes/no)
- Approach: Laparoscopic, robotic, open
- Extended resection
- Conversion to open surgery (yes/no)
- Anastomotic configuration (stapler anastomosis, hand-sewn; end-to-end; side-to-end; pouch to end)
- Number of stapler cartridges used
- Intra- and postoperative complications
- Anal verge distance (cm) from the tumor lower edge [12, 22, 24-27, 32, 38]
- Anal verge distance (cm) from the anastomosis [12, 22, 24-27, 32, 38]
- Circumferential margin (mm)
- Protective ostomy (yes/no)
- Type of anastomotic testing
- Postoperative leucocyte count and CRP level up to 10 days postoperative
- Date of discharge and discharge status
- Indication (Neoplasia, IBD, perforation, diverticulitis, mesenterial ischemia)
- In case of rectal cancer, preoperative carcinoembryonic antigen (CEA, ng/ml) and pathological TNM staging according to TNM 8th edition (T, N, M, L, V, Pn, grading (high, low), resection status (R0, R1, R2)
- In case of rectal cancer length of follow-up, disease-free and overall survival

Sample Size

While even the largest cohort with millions of patients cannot ascertain a perfect clinical prediction model if no significant input variables are included (“garbage in, garbage out” – do not expect to predict the future from age, gender, and body mass index), the relationship among predictive performance and sample size is certainly directly proportional, especially for some data-hungry ML algorithms. Moreover, to protect the generalizability of the clinical prediction model, the sample size must be both representative enough of the patient population and should consider the complexity of the algorithm. For instance, a deep neural network – as an example of a highly complex model – will need thousands of patients to assemble, while a logistic regression model may accomplish stable results with only a few hundreds of patients. In addition, the number of input variables has a role to play. Roughly, it can be said that a bare minimum of 10 positive cases are needed per included input variable to model the relationships. Often, eccentric behavior of the models and high variance in performance among splits is noted when sample sizes are smaller than calculated with this rule of thumb. Of immense importance is also the proportion of patients who suffered the outcome. For very rare events, a much larger total sample size is required. For example, a prediction based on 10 input features for an outcome occurring in only 10% of cases would need at least 1000 patients including at least 100 who suffered the outcome, according to the above rule of thumb.

In general, from personal experience, we do not propose producing ML models on cohorts with less than 100 positive cases and wisely more cases in total, regardless of the rarity of the outcome. Also, one should examine the available literature on risk factors for the outcome of interest: If epidemiological studies acquire only feeble associations with the outcome, it is probably that one will need plenty more patients to reach a model with satisfactory predictive performance, as opposed to an outcome which has several highly associated risk factors, which may be easier to predict. Bigger sample sizes also permit more generous evaluation through a larger amount of patient data dedicated to training or validation, and usually results in superior calibration measures.

For this study, based on our expertise and on the rules of thumb mentioned above, we approximated that a minimum of 250 patients with AI are needed to identify generalizable features. With an incidence of AI of 5% for colon anastomosis and 8% for colorectal anastomosis, that means that a minimum of 5000 and 3125 patients are required for training for each population (colocolic and colo-rectal anastomosis, respectively). For satisfactory evaluation of calibration at external validation, we estimate that another 2000 and 1250 patients per cohort (thus, approximately 100 with AI per cohort) will be required. Thus, in total, we estimate that **7000 (colocolic anastomosis) and 4375 (colorectal anastomosis) patients** are necessary to reach at a satisfying model. More data will likely lead to greater performance and better calibration.

Predictive Modeling

A KNN imputer will be co-trained to impute any missing data that may occur in future application of the model. If there is missing data in the training set, it will be imputed using said KNN imputer. [39] Features or patients with a missingness greater than 25% will be excluded. Data will be standardized and one-hot-encoded. In case of major class imbalance – which is expected for the abovementioned endpoint – random upsampling or synthetic minority oversampling (SMOTE) will be applied to the training set. [40, 41] All features will at first be given to the model for training. If needed, we will employ recursive feature elimination (RFE) to choose input features on the training data. [42]

We will trial the following algorithms for binary classification: Generalized linear model (GLM), generalized additive model (GAM), stochastic gradient boosting machine (GBM), naïve Bayes classifier, artificial neural network, support vector machine (SVM), and random forest. Each model will be fully trained and hyperparameter tuned where applicable. The final model will be selected based upon (AUC), sensitivity, and specificity, as well as calibration metrics on the resampled training performance. Training will happen in repeated 5-fold cross-validation with 10 repeats.

The one final model will then be examined on the external validation data only once. Ninety-five percent confidence intervals for external validation metrics will be derived using the bootstrap.

The threshold for binary classification will either be identified on the training data alone using the AUC-based “closest-to-(0,1)-criterion” or Youden’s index to optimize both sensitivity and specificity or will be optimized on the training set based on clinical significance (rule-out model). The analyses will be carried out in R Version 3.6.2. [43] or Python.

Evaluation

The efficacy of classification models can be approximately evaluated along two dimensions: Model discrimination and calibration. [44] The term *discrimination* denotes the ability of a prediction model to correctly classify whether a certain patient is going to or is not going to suffer a certain outcome. Thus, discrimination describes the accuracy of a binary prediction – yes or no. *Calibration*, on the other hand, defines the degree to which a model’s predicted probabilities (ranging from 0% to 100%) correspond to the observed incidence of the binary endpoint (true posterior). Many publications do not report calibration metrics, although these are of central importance, as a well-calibrated predicted probability (e.g. your predicted probability of experiencing a complication is 18%) is often much more valued to clinicians – and patients! – than a binary prediction (e.g. you are likely not going to experience a complication). [44]

Resampled training performance as well as performance on the external validation set will be examined for discrimination and calibration. In terms of discrimination, we will assess AUC, accuracy, sensitivity, specificity, positive predictive value (PPV), negative predictive value (NPV), and F1 Score. In terms of calibration, we will assess the Brier score, expected-observed (E/O) ratio, calibration slope and intercept, the Hosmer-Lemeshow goodness-of-fit test, as well as visual inspection of calibration plots for both datasets, which will also be included in the publication.

Interpretability

The degree and choice of methods for interpretability will rely upon on the final chosen algorithm. Some algorithms can natively give explanations as to which factors affect the outcome in what way. Thus, in case e.g., a GLM, GAM, or naïve Bayes classifier is chosen, the parameters / partial dependence values will be provided. For simple decision trees, diagrams of the decision-making process can be given. Other models with higher degrees of complexity, such as neural networks or stochastic gradient boosting machines cannot natively provide such explanations. In that case, we will provide both AUC-based variable importance as well as model-agnostic local interpretations of variable importance using the LIME principle. [45]

Expected Results

We foresee arriving to a generalizable model based on multicenter international data that is likely to predict AI consistently with an AUC of at least 0.70 (more realistically 0.8 or greater) and that is well-calibrated. [44] A web-based prediction tool will also be designed for each of the two models applying the *shiny* [46] environment, much likened to e.g., <https://neurosurgery.shinyapps.io/impairment>. This web-based app will be accessible for free on any internet-capable device (mobile or desktop), and should be stable on most devices due to the server-based computing. The costs for maintaining the server will be carried by the main investigators.

The assembled data will be saved for 10 years by the sponsor. The large dataset will be available to further analysis and will be given to any of the participating centers at request and after approval by all other centers. The goal is to facilitate other analyses using the collected dataset. If any other analyses reach publication, all contributors will be included as co-authors and all co-authors will have the opportunity to review said manuscript beforehand. Any contributing study center has the right to veto publication of any subsequent analyses containing their own data.

Acknowledgement: The study idea and the study protocol were developed together with [name] (Machine Intelligence in Clinical Neuroscience (MICN) Laboratory, Clinical Neuroscience Center, University Hospital Zurich).

References

1. Lee, S.W., D. Gregory, and C.L. Cool, Clinical and economic burden of colorectal and bariatric anastomotic leaks. *Surg Endosc*, 2019.

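### Does the six-week loss exclusion need to say whether patients with a leak confirmed before loss stay in?

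*Protocol*

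**What the plan says.** Under Inclusion and Exclusion Criteria, "patients who were lost to follow-up less than six weeks after surgery and who have not noted a successful ostomy reversal will be excluded". The reason follows directly: "in these cases, it cannot be surely assessed whether AI occurred or not".

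Under Primary Endpoint Definition, AI is defined "as any clinical signs of leakage, confirmed by radiological examination, endoscopy, clinical examination of the anastomosis, or upon reoperation". No minimum follow-up is required for a positive finding. Under Secondary Endpoint Definitions, death in AI cases "will be recorded within 90 days from index surgery", and days from operation to diagnosis of the leak are calculated for AI cases.

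The lists under Features and Their Definitions include discharge date and status for everyone and whether a protective ostomy was made. They do not include its reversal. Length of follow-up is listed for cancer only: "In case of colon cancer length of follow-up, disease-free and overall survival" and "In case of rectal cancer length of follow-up, disease-free and overall survival". Data Collection says that the sponsor will issue a standardized form, which is not part of the document.

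**The concern.** Take a patient whose leak is confirmed on day 8, who is lost to follow-up in week 4, and for whom no ostomy reversal is noted. The rule removes this patient. Its reason does not reach the patient, whose AI status is known. One centre could follow the words and another the reason.

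The difference depends on the outcome, because only AI patients are affected. If training and validation centres differed in practice, the observed AI rate would shift between the two sets. The shift would fall on the E/O ratio and calibration intercept that the Evaluation section promises to report. It also seems hard to detect afterwards: the lists show no ostomy reversal, and outside cancer no length of follow-up. A later analysis plan cannot recover patients who were never entered.

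**Working it through.** **The plan's own figures.** From Sample Size: 250/0.05 = 5000 and 250/0.08 = 3125 for training; 100/0.05 = 2000 and 100/0.08 = 1250 for validation. The totals are 7000 and 4375, as stated. Nothing in this point alters them.

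**Assumptions.** The protocol gives no loss rates, so let
- x = share of AI patients confirmed, then lost before six weeks with no reversal noted;
- z = share of AI patients lost early before confirmation;
- y = share of non-AI patients lost early.

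**Effect of each reading on the AI odds.**
- Rule as written: factor (1 − x − z)/(1 − y).
- Exception for confirmed AI: factor (1 − z)/(1 − y).

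With equal total loss, x + z = y, the first factor is 1 and incidence stays at 5% and 8%. The exception reading is undistorted only if z = y. With z = 0 and y = 5%, the colocolic odds 0.05/0.95 are divided by 0.95, giving 5.25%; the colorectal figure becomes 8.39%. With z = 3% and y = 5%, the figures are 5.10% and 8.15%. So the rule as written is not the inferior choice: making an exception keeps known events but selects on the outcome.

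**Gap between the readings, taking z = 0.** If all training centres used one reading and all validation centres the other, the logit shift is −ln(1 − x). If a share k of patients in a set comes from centres that make the exception, that set's factor is [1 − x(1 − k)]/(1 − y). The shift is then ln{[1 − x(1 − k₁)]/[1 − x(1 − k₂)]}, which is zero when k₁ = k₂. The middle column takes k₁ = 0.7 and k₂ = 0.3.

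| x | Shift, wholly opposite readings | Shift, 70% v 30% | AI cases dropped by the rule as written, of 250 / of 100 |
|---|---|---|---|
| 2% | 0.020 | 0.008 | 5 / 2 |
| 5% | 0.051 | 0.021 | 12.5 / 5 |
| 10% | 0.105 | 0.042 | 25 / 10 |
| 20% | 0.223 | 0.089 | 50 / 20 |

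**Yardstick.** With 100 events and constant predicted risk, the 95% half-width of the calibration intercept is 1.96/√(100(1 − p)), which is 0.201 at p = 0.05 and 0.204 at p = 0.08. Spread in predicted risk lowers the information, so these are lower bounds. A shift equal to the half-width needs x = 1 − exp(−0.201) = 18.2%, or 18.5% for colorectal, with wholly opposite readings. The standard error is 0.201/1.96 = 0.103. The 10% row is therefore about one standard error in the extreme case (0.105/0.103) and about 0.4 in the 70/30 case (0.042/0.103).

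**The case for a change.** The strongest argument for a change is that eligibility is protocol content, applied by each centre and partly in retrospect. A patient who was never entered leaves no trace that a later document could use. A shift below the sampling half-width is also not automatically harmless: it is a bias, and at x = 10% with opposite readings it would be about one standard error. The cure looks cheap, at one clause and two data items. Finally, the criterion does not say whether early death counts as loss, and AI patients with a takedown may be less likely to have a reversal noted.

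Part of this stands. The wording and its reason do diverge for this patient, and a clarifying clause would do no harm. The rest is weaker.

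- The text is not silent. It excludes, and the clause after the dash explains the rule without adding a second test.
- The reading used is not wholly hidden. A cancer patient with AI, under six weeks of follow-up and no protective ostomy shows that the centre kept such cases. The check is one-sided, since the absence of such patients proves nothing, and it does not cover other indications.
- Last contact and ostomy reversal are items for the collection form, which may well hold them. A comparison with and without these patients is ordinary material for an analysis plan. Neither document is shown.
- No passage treats death as loss. Recording death to 90 days in AI cases presupposes that those who die early remain in the data, so analysts would ordinarily count a death as observed.

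**Conclusion.** No change is needed. There is a small mismatch between a rule and its explanation, but following the rule as written gives a sound cohort, with undistorted incidence when early loss is equal in AI and non-AI patients. Making an exception for confirmed AI can also be defended, but it is not clearly better, because it can raise the apparent incidence.

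On assumed values of x from 2% to 10%, the gap between readings is at most 0.020 to 0.105 logits, against a sampling half-width of at least 0.20. It shrinks quickly once both sets contain centres of either kind. It would exceed sampling error only if more than about 18% of AI patients were confirmed and then lost within six weeks, with training and validation centres wholly opposed. Nothing in the protocol suggests this, and its 90-day record of death in AI cases implies that these patients are traced well beyond six weeks.

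The conclusion rests on those assumed rates. It also assumes that the unseen form and analysis plan deal with last contact and early loss in the usual way.

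### Nutrition and renal function are collected only as categories, without the score or value behind them, and albumin is entered both as a value and as its own cut-off

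*Protocol*

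**What the plan says.** The Protocol's Features and Their Definitions has one list per model.

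- **Renal function** is a five-level stage in both: "Renal function (CKD Stages G1 (normal) to G5) [7" for colocolic and "Renal function (CKD Stages G1 (normal) to G5) [7, 33" for colorectal anastomosis. Neither list contains creatinine or eGFR.
- **Nutrition** is a single cut-off in both: "Nutritional status (NRS ≥ 3) [16" and "Nutritional status (NRS ≥ 3) [16, 34". The NRS total is not listed.
- **Albumin** appears twice in both. One item is the flag "Hypoalbuminemia (<3.5 g/dL) [17-19". The other has no cut-off and is read here as the measured value: "Albumin and Prealbumin" in the colocolic list and "Albumin/Prealbumin" in the colorectal list.
- **Haemoglobin, leukocyte count and age** are taken as measured values, so cut-offs are not the Protocol's general practice.

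Under Predictive Modeling, "Data will be standardized and one-hot-encoded". Missing values are filled by a KNN imputer that is also meant for later use of the model. Features or patients with more than 25% missing are dropped. All features go into training first, with recursive elimination only if needed.

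**The concern.** Encoding, and the order of derivation and imputation, can be settled in an analysis plan. What the centres are asked to record cannot. Once the standardized form has collected a yes/no at NRS 3 and a CKD stage, no later analysis can rebuild the score or the eGFR from the pooled data. The data are also meant to be saved for ten years and offered for further analyses, so the choice outlasts these two models.

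Three things are at stake. The first is predictive information in nutrition and, less so, in renal function. The second is model columns spent on stages with very few leaks, if the stage is split by one-hot encoding. The third is a duplicate albumin input, whose two fields could disagree after imputation, both in training and when a web-tool user leaves one blank.

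**Working it through.** **The plan's own figures (Sample Size).** Training: 250 / 0.05 = 5000 colocolic and 250 / 0.08 = 3125 colorectal. Validation: 2000 × 0.05 = 100 and 1250 × 0.08 = 100 leaks. Totals: 5000 + 2000 = 7000 and 3125 + 1250 = 4375. All reproduce exactly, and nothing below changes them.

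**NRS cut-off.** Assume an approximately normal underlying score with a linear effect. A cut-off that classes a proportion p as positive keeps φ(c)² / [p(1 − p)] of the linear information, where c is the normal quantile for p and φ the normal density. The Protocol does not give p, so a range is shown. The AUC column simulates one predictor in 1,000,000 patients with log-odds 0.5 per SD and leaks in about 5%. The continuous score then has AUC 0.636.

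| Assumed share NRS-positive | Information kept | Univariable AUC of the flag |
|---|---|---|
| 10% | 34% | 0.556 |
| 20% | 49% | 0.581 |
| 30% | 58% | 0.594 |
| 40% | 62% | 0.598 |

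With log-odds 0.3 per SD the AUC falls from 0.581 to 0.530-0.557. With 0.7 it falls from 0.688 to 0.584-0.635. These are univariable figures. The loss in a full model would be smaller, because albumin, prealbumin and BMI are also collected.

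**CKD stage.** For several ordered categories, the information kept is Σ [φ(c_{k−1}) − φ(c_k)]² / s_k, where s_k is the share in stage k. Stage shares are not in the Protocol. Assumed shares for G1 to G5:

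- 75 / 18 / 6 / 0.7 / 0.3%: 59% kept
- 60 / 30 / 8 / 1.5 / 0.5%: 72% kept
- 45 / 40 / 13 / 1.5 / 0.5%: 80% kept (0.795)
- 30 / 45 / 22 / 2 / 1%: 85% kept (0.845)

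For the third distribution, the simulated AUC with the stages kept in order is 0.618, against 0.636 for the continuous value (log-odds 0.5).

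**Leaks per stage if one-hot encoded.** Expected training leaks = N × stage share × leak incidence. Since 5000 × 0.05 = 3125 × 0.08 = 250, a stage reaches 10 leaks at average risk only if it holds at least 10 / 250 = 4% of patients, in either model. At an assumed stage share of:

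- 0.5%: 25 colocolic or about 16 colorectal training patients, and 1.25 expected leaks in either model
- 1%: 50 or about 31 patients, and 2.5 leaks
- 2%: 100 or about 63 patients, and 5 leaks

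Doubling the risk in that stage doubles the leaks, to 2.5-5 at 0.5-1%. In either validation cohort, 0.5-1% gives 0.5-1 leak at average risk. The Protocol states its ten-event rule per input variable. Applying it per encoded column is a reading of that rule.

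**Albumin.** The flag is a function of the value, so it adds no measurement. Predictive Modeling states no rule that links the two fields. Whether imputation can make them disagree depends on settings that are not given. If the same neighbours serve both fields, k is odd, the value is filled by the median and the flag by majority, they cannot conflict. If the value is filled by the mean, a few high neighbours can lift it to 3.5 g/dL or above while most neighbours are flagged.

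**The case against.** The strongest reply is that little here is an error. Five ordered stages are not a cut-off, and they retain most of the renal information. Albumin, prealbumin and BMI carry much of what NRS would add. Stage prevalences are assumptions. How ordinal items are encoded and how linked fields are imputed are matters for an analysis plan, which is not shown. Recursive elimination may drop weak or duplicate inputs, and a sparse column is not shown to harm the candidate algorithms. Centres keep a log linking study numbers to their own patient numbers, so source values could be retrieved. Some records may hold only the category, and a raw item missing in more than 25% would be excluded under the Protocol's own rule.

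Much of this stands, and it limits the point. A reader might infer the following, which the document does not support:

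- **The renal gradient is discarded.** It is coarsened. Its order is also lost if the stage is one-hot encoded.
- **Near-empty columns are certain.** They depend on stage shares and on an encoding that the Protocol does not spell out for ordinal items.
- **The imputer fills the two albumin fields independently.** The text does not say so. Conflicting pairs are possible, not shown.
- **Recording creatinine solves acute rises in emergency patients.** A single creatinine is affected by the same rise.
- **Height and weight must go because BMI is present.** That is modelling preference.

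The reply does not answer the collection choice itself. An analysis plan cannot derive a score or an eGFR from a category, and returning to the charts through the centre logs would cost far more than recording the number at first entry.

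**Conclusion.** The point holds as a minor weakness in what is collected. The NRS cut-off is the larger loss: about 34-62% of linear information is kept if 10-40% of patients are positive, partly offset by the other nutritional items. CKD staging is the smaller loss, with about 59-85% kept over four assumed distributions. Sparse stage columns are conditional on one-hot encoding and arise, by the ten-leak yardstick, for any stage under 4% of patients at average risk. The second albumin field is redundant, with a possible but unproven inconsistency after imputation. The percentages rest on a normal predictor with a linear effect and on prevalences absent from the Protocol. They show scale and do not forecast the loss in the final models, which has not been quantified.

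**What to change.** On the data form for both models:

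1. Record the NRS total score. Keep the category at 3 as a separate fallback field, used only where no score exists.
2. Record the preoperative creatinine with its unit, derive eGFR centrally by one stated formula, and enter it as one continuous input in place of up to five stage columns. Keep the CKD stage only as a fallback.
3. Use the albumin value, with its unit, as the only albumin input. Derive the hypoalbuminemia flag from it after imputation, for descriptive tables only.

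The cost is a change to the form and data dictionary, with a number entered where a category is now asked for. The planned sample sizes do not change. The downside is that some retrospective records will hold only the category. The availability of raw values should therefore be checked by centre early on, because a raw item missing in more than 25% would be dropped under the existing rule and the category would then have to serve.
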